6.2.13 Visit 13 – Phase 2 Start: Intervention or Control

Near the end of the 7th study week, participants have an in-person study visit to be equipped with abbreviated PSG monitoring. Overnight recording is initiated.

Above procedures take about 1 hour 'active' engagement to complete.

-Participant returns home (if applicable) and is continuously monitored throughout the subsequent remaining day and overnight with PSG

6.2.14 Visit 14 (Phase 2)

Study team members visit the participant the following morning to remove PSG.

Above procedures take about 30min 'active' engagement to complete.

6.2.15 Visit 15 (Phase 2)

Near the end of the 8th study week, participant is re-equipped with abbreviated PSG. Overnight recording is initiated.

Above procedures take about 1hr 'active' engagement to complete.

-Participants returns home (if applicable) and is continuously monitored throughout the subsequent remaining day and overnight with PSG.

6.2.16 Visit 16 (Phase 2)

Study team members visit the participant the following morning to remove PSG.

-Participant returns sleep pad system (including pad and controller).

Above procedures take about 30min 'active' engagement to complete.

6.2.17 Visit 17 (Phase 2)

Participant has a fasted blood draw conducted by qualified Clinical Research Center (CRC; Noll Laboratory) staff. This visit (17) may be combined with the previous visit (16) if a participant elects for the blood draw to occur in their personal residence.

Upon completion, participants receive a ~1min survey to assess both their awareness of their assigned condition order and so that they have the opportunity to request to be contacted with information about their randomized order after the study concludes (please refer to CATS attachment, "End of Study Survey"). Participants also receive an optional ~1min survey via email that is administered through REDCap shortly after ending participation (please refer to CATS attachment, "Follow-Up Survey").

Above procedures take about 30min 'active' engagement to complete.

6.3 Duration of Participation

Screening Consent activities are expected to take about 30min to complete (including initial remote electronic survey and in-person activities at the first study visit). One session expected (secondary screening), with another session optional (if not qualifying on abbreviated MoCA).

Consent activities are expected to take about 1hr to complete. One session is expected, with additional optional session(s) if a participant decides they want more time to consider during a session.

Overall study timeline after Consent concludes is approximately 8wks. During those 8wks, active study engagement by a participant is expected to take about 15hrs, with an expected 17 in-person sessions. That time is spread out across study parts in about the following distribution:

Baseline (week ~1): ~4.5hrs with 6 sessions (visits 1-6 above) including surveys

Part 1 (weeks ~2-4): ~5hrs (weighted towards weeks 3 & 4) with 5 sessions (visits 7-11 above) including surveys

Washout (week ~5): ~30min with 1 session (visit 12 above) including surveys

Part 2 (weeks ~6-8): ~5hrs (weighted towards weeks 7 & 8) with 5 sessions (visits 13-17 above) including surveys

6.4 Test Article(s) (Study Drug(s) and/or Study Device(s))

6.4.1 Description

The test article in this study is an investigational device. The pad portion is designed to be placed onto a bed beneath a fitted sheet in a specific orientation relative to a pillow and slept upon. The pad is powered with an attached bedside device, applies a safe range of magnetic waves. The stimulation is hypothesized to improve sleep duration and quality.

The Sleep Pad system has undergone preliminary review by the FDA (please refer to CATS attachment, "FDA Review Meeting Minutes") and received enthusiasm for empirical evaluation in this particular protocol as an intervention. According to published FDA device categorization guidelines (please refer to CATS attachment, "FDA Risk Categorization Guidelines," particularly pg.3 after title pg.) and in light of electromagnetic safety data (please refer to CATS

attachments, "Electromagnetic Field Safety Testing" and "FCC Compliance Test Statement"), this study's PI considers the Sleep Pad system to be Not of Significant Risk (NSR). The device should not be used with powered covers (e.g. heating pads) nor on water beds, although there are not known risks to doing so. Other radiofrequency signals in the sleeper's environment may overpower/wash-out the low level magnetic field generated by the pad, so it is recommended to turn off or remove any modem/router located in the bedroom and to put cellular devices into airplane or Do Not Disturb mode during Sleep Pad system use for optimal effect, although there are not known risks to having such devices in use with the Sleep Pad.

6.4.2 Treatment Regimen

Treatment dosing is under participant control, by physical proximity/orientation to the pad portion of the Sleep Pad system, and by a manually operated power button on the bedside controller portion of the Sleep Pad system. Dosing is scheduled to occur throughout the participant's typical nocturnal sleep period, nightly during the Intervention (either phase I or phase II, depending upon randomization) of the research. The range will be preset to the minimum setting by researchers, and participants will be instructed to not change the settings. Participants verify their "dose" settings by attesting to not having changed settings implemented by researchers in nightly REDCap surveys.

6.4.3 Method for Assigning Subject to Treatment Groups

All participants in this study will experience all study conditions (i.e. a sham (Control) and an active (Intervention) Sleep Pad bedside controller), in a randomized crossover design. The random assignment to intervention order (Sham Sleep Pad System vs. Activated Sleep Pad System at Part 1; reverse at Part 2) will be completed in REDCap, with replacement for early withdrawal, and intention to assign 50% of participants to each study condition order. Participant recruitment will not be stratified, but randomization to a study condition order will be gender-stratified to ensure balanced assignment of males and females (assigned at birth) between condition orders.

[name] is the designated team member who will implement and hold the blind related to these randomization procedures; he does not interact directly with participants. Once randomized, an appropriate Sleep Pad controller ID is designated for use and shared with blinded study team members. The linking list of controller IDs and their settings (activated vs deactivated) is confidentially maintained by the Sponsor and [name] unless specific study events require lifting the blind.

6.4.4 Subject Compliance Monitoring

Participants will complete nightly REDCap surveys self-attesting adherence to the protocol during Control/Intervention (Phases 1 & 2) that are shared with the research team as data to confirm Sleep Pad use.

6.4.5 Blinding of the Test Article

This study is a double-blind trial, in which bedside controllers for Sleep Pad systems are coded and either "activated" or "deactivated" (sham) by the manufacturer prior to receipt (in two sets) for use in the research. A "deactivated" bedside controller retains all functionality (and evidence of functionality) of an "activated" bedside controller, excepting the stimulation. The blind is

maintained by a designated study team member who will have access to the list linking device code IDs to their relative active/sham group, and who does not have interaction with study participants. This blind will be lifted if relevant for safety reasons in cases of serious adverse event on a participant case-by-case basis, and on the whole for other researchers after completion of the entire trial for data analysis.

6.4.6 Receiving, Storage, Dispensing and Return

6.4.6.1 Receipt of Test Article

The pad portion of the Sleep Pad system is interchangeable, so a participant will receive and use only one throughout their study. Participants receive two different bedside pad controllers during the course of the study, one at a time; once each for Phase 1 and Phase 2 (Control/Intervention). The bedside controller device code corresponding to a given participant ID and Phase will be documented for later data analysis. Participants receive in-person instruction regarding Sleep Pad system setup upon receipt, and also print and/or electronic instructional materials.

6.4.6.2 Storage

The pad portion of the Sleep Pad system is interchangeable between bedside controllers and can only be "used" (i.e. apply magnetic field) when equipped with a corresponding "activated" bedside controller. Bedside controllers will be stored in the laboratory space and code-labeled according to their internal settings (i.e. one set with codes corresponding to "activated" and one set with codes corresponding to "deactivated," but to which all Investigators except one are blinded). Pad portions of the Sleep Pad system will be stored separately from bedside controllers until being provided to a study participant. Participants maintain the "pad" portion of the Sleep Pad system throughout the study. Participants will be instructed that only research participants in the study should use the device as directed, and that no individual should attempt to use the device inconsistent with directions. a person in physical proximity to the pad is not expected to have any "exposure" to its signal unless it is used as directed.

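### Could a safety unblinding of one participant reveal everyone else's treatment order, because the controllers arrive and are labelled in two sets?

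*Combined protocol and SAP*

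**What the plan says.** The manufacturer fixes each bedside controller as active or sham and codes it "prior to receipt (in two sets) for use in the research" (section 6.4.5). On storage, section 6.4.6.2 says "Bedside controllers will be stored in the laboratory space and code-labeled according to their internal settings". It then explains that one group of codes stands for active and the other for sham, and adds "but to which all Investigators except one are blinded".

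After randomization, "an appropriate Sleep Pad controller ID is designated for use and shared with blinded study team members" (section 6.4.3). The list that links IDs to settings "is confidentially maintained by the Sponsor" together with one team member who has no contact with participants. Sections 6.4.5 and 6.4.6.3 mention only that team member.

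On use, "Participants receive two different bedside pad controllers during the course of the study, one at a time" (section 6.4.6.1), and "The bedside controller device code corresponding to a given participant ID and Phase will be documented for later data analysis" (same section). Controllers come back at Visit 11 (section 6.2.11) and Visit 16 (section 6.2.16), and all devices go back to the Sponsor/manufacturer when the study ends (section 6.4.6.4).

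On unblinding, "This blind will be lifted if relevant for safety reasons in cases of serious adverse event on a participant case-by-case basis" (section 6.4.5). Other researchers learn the allocation only after the whole trial is complete. Section 9.6 likewise confines early unblinding to serious reactions.

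**The concern.** Blinded staff handle labelled devices and hold a record of who had which code in which phase. The clause about blinded Investigators can be read in two ways. It may mean that they do not know which set a controller belongs to. It may also mean only that they do not know which of two visible sets is the active one. On the second reading the two sets form a single shared secret, and learning the status of one controller gives away both. The crossover sharpens this, because each participant uses one active and one sham controller, so one known setting fixes that person's whole order.

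A returned controller reissued under the same code would be another route, and no section rules that out. The protection of the remaining participants would then fail at the first safety unblinding. Later judgments about whether the device caused an adverse event (section 9.3) could be made with the order known.

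**Working it through.** The plan gives no figure to reproduce. The check is a count, followed by a reading of the sections side by side.

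**Inputs.** Target of 10 completers (section 7.1). Two controllers per participant, one per phase (section 6.4.6.1). Unblinding one participant at a time for a serious event (sections 6.4.5 and 9.6). Number of controllers supplied: not stated.

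**Bounds on the number of other participants revealed.**

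- Sets recognisable: one controller of known status identifies both sets, so 10 − 1 = 9 others. This holds for a Phase 1 event as well, when only one controller has been issued.
- IDs uninformative and each controller issued once: 0 others. This takes 10 × 2 = 20 controllers, plus 1 or 2 for each replaced participant, depending on the phase in which that participant left.

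**Between the bounds.** Assume, without support in the plan, that IDs are uninformative but controllers are reissued at random from k per setting, and that both of one participant's controllers become known. The expected number of others directly revealed is 9 × (1 − (1 − 1/k)²):

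- k = 1: 9 × 1 = 9
- k = 2: 9 × 0.75 = 6.75
- k = 5: 9 × 0.36 = 3.24
- k = 10: 9 × 0.19 = 1.71

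Following links onward through the participant-by-phase record raises the last three to 8.99, 7.98 and 3.66 (20,000 simulated runs). The result depends almost wholly on k, which is unknown, so these values describe the assumption and not this trial.

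**Which reading the text favours.**

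1. Sections 6.4.3, 6.4.5 and 6.4.6.3 all describe a list at the level of the individual ID. If sets were recognisable, one line saying which set is active would do.
2. Section 6.4.3 has a specific ID designated after randomization and passed to blinded staff. They need not choose from a set or know that sets exist.
3. The blinding clause in section 6.4.6.2 directly qualifies the sentence about codes. Its natural object is the correspondence between code and setting.
4. Arrival in two sets need mean no more than that two kinds of controller were made.
5. Section 6.4.6.4 allows for unused controllers at the end, which suggests spare stock, although it does not exclude reissue.

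**What must hold together for harm.** (a) Sets are recognisable, or controllers are reissued under the same code. (b) A serious event leads to unblinding. (c) The disclosure reaches someone who also judges other participants. (d) Some of those participants are still to be judged. The plan states neither limb of (a). Section 9.7 records that the Investigators consider the study minimal risk, which bears on (b). The count of 9 covers all other participants, while (d) leaves only some of them; the documents give no accrual pattern from which to find how many.

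**The case for a change.** The strongest case for acting is that the protection is implied and not stated. The clause names Investigators, whereas other staff also handle the devices. No sentence says that codes hide set membership or that a returned controller is not reissued. In a crossover with 10 participants, a leak could be complete, and a sentence or two would remove the doubt. It is true that the text is silent on these points. Silence about label format is nevertheless a matter of detail in a protocol of this kind, and the person holding the key is well placed to deal with it.

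The documents also do not say who scores the sleep recordings or when, so one cannot prove that only causality judgments would be exposed. That route still needs conditions (a) to (c), with the scorer as the person informed. Participants are not themselves unblinded this way, so their insomnia scores and diaries are not directly affected.

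Two neighbouring points add little. Section 6.4.3 names the Sponsor as a holder of the key where sections 6.4.5 and 6.4.6.3 do not, but neither of those says the team member is the only holder. No section promises a blinded Sponsor, and the manufacturer must know settings that it applied itself. Second, section 6.2.12 speaks of the participant getting the bedside controller back in week 6, while section 6.4.6.1 has two different controllers. Since each controller's setting is fixed before receipt and every participant has both conditions, section 6.4.6.1 must be what is meant. This is loose wording.

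**Conclusion.** No change to the plan follows. The sections on blinding and storage are compatible with individually scrambled, single-use codes, under which unblinding one participant reveals none of the other 9. The contrary reading, which could reveal all 9, is possible but is not what the text says. The range from 0 to 9 covers every possible value, so it gives no evidence of a leak of any particular size.

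This is missing operational detail that the blind-holder can fill sensibly when designating IDs. The conclusion assumes that the codes do not show set membership to staff who handle the devices, and that no controller goes to a second participant under an unchanged code. If either assumption failed, a serious event would still have to occur, and its disclosure would have to reach someone judging other participants, before any assessment was affected. The route identified runs mainly to later causality judgments, so following the plan as written leaves the trial's comparisons sound.

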6.4.6.3 Preparation and Dispensing

Participants will be randomly assigned to their crossover order (i.e. to their order of using an "activated" or a "deactivated" bedside controller). Activation or deactivation and coded device ID(s) are applied to the bedside controller portion of the Sleep Pad system by the manufacturer, prior to receipt by researchers. Researchers receive coded controllers. A list linking device IDs to their settings, and thereby the blind, is maintained by a designated study team member. "Administration" of the Sleep Pad system occurs when a participant lays upon the pad portion of a system that includes an activated bedside controller, which they have turned on manually, consistent with contact/orientation instructions (as designated in setup instructions).

6.4.6.4 Return or Destruction of the Test Article

The Sleep Pad systems (bedside controller devices [used or unused] and pad portions) will be returned (i.e. shipped) to the Sponsor/manufacturer at the conclusion of the study.

6.4.6.5 Prior and Concomitant Therapy

Participants must be willing to refrain from initiating new, sleep-directed interventions (e.g. medication; behavioral) that are not a part of this study protocol for the duration of study participation. Taking any physician-directed pharmacologic intervention for sleep or being actively engaged in a clinically-validated course of therapy (including behavioral therapy for sleep) is an exclusion criterion.

7.0 Number of Subjects and Statistical Plan

7.1 Number of Subjects

We expect to evaluate up to 35 participants in screening qualification, aiming to initially identify up to 20 eligible individuals according to the screening procedures. Screening evaluations will pause at that time by pausing both the REDCap survey availability and by our otherwise manual control of release of the screening survey REDCap link until it is determined by Investigators that additional recruitment is necessary (e.g. to replace participant drop-outs or if failure to identify 20 eligible individuals occurs). Should recruitment need to be re-opened beyond 35 participants an IRB Protocol modification would occur, expecting to regulate future screening qualification in specific intervals to reduce risk of unnecessary screening of individuals. We aim to complete 10 subjects in this study.

7.2 Sample Size Determination

This pilot study is being used to determine feasibility and effect sizes, therefore no information is available upon which to estimate a minimum necessary sample size. This study will inform the sample size of future studies and proposals.

7.3 Statistical or Analytic Methods

Primary and secondary outcomes will be compared between sleep pad conditions, within participants, as a change score relative to their own Baseline.

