1.0 Objectives

1.1 Study Objectives

We propose to examine the potential effects of the Frequen-ZZZ/Sleepergize sleep pad – a noninvasive, unobtrusive appliance that generates a magnetic gradient, and that is used on the bed – on multiple sleep outcomes in an 8-week randomized crossover study, and to calculate the effect sizes of the intervention to inform power and sample size for future studies.

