6.0 Study Design and Procedures

6.1 Study Design

This 8-week, randomized, cross-over, at-home clinical trial of mid-life adults (men and women aged 40-65 years) consists of four segments: Baseline (week 1), active Intervention/Control (weeks 2-4), Washout (week 5), and active Intervention/Control (weeks 6-8).

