6.2 Study Procedures

General overview

Participants complete Screening Consent in REDCap and, if eligible based on screening surveys, schedule their consent appointment and study dates.

Participants complete an Informed Research Consent in-person with study staff. Participation in the ~8wk study begins immediately after completion of this consent.

Throughout the entire ~8wk study:

- -Ambulatory sleep measurement (via wrist-worn actigraphy, day and night ~24hrs)
- -Twice daily self-assessment of sleep, related activities, and device usage (via REDCap sleep diaries [~1min each, totaling ~2min daily]) administered in the morning ("Morning" survey in CATS) and evening ("Bedtime" survey in CATS)
- -Weekly REDCap surveys (participants receive survey link at either/both their personal email or phone number [by text message], according to their preference; ~15min each). Participants may choose to receive email or text message reminders, or phone/voicemail reminders, to their personal accounts/devices about surveys
- -Responding to questions by staff during each study visit to determine ongoing qualification and possible study events

Overview of 4 study parts (details in below, specific sections):

- -"Baseline": Baseline data collection without sleep pad device present/in-use (week ~1) and randomization. Objective sleep monitoring for 2 nights. Blood sample (up to 40cc / up to 3 tablespoons) collected.
- -"Phase 1": Active intervention/control with either the sleep pad or an identical-looking/operated 'sham' pad present/in-use nightly (weeks ~2-4). Objective sleep monitoring for 2 nights. Blood sample (up to 40cc / up to 3 tablespoons) collected.

- -"Washout": Break from presence/use of the sleep pad device (week ~5)
- -"Phase 2": Active intervention/control with either the sleep pad or an identical-looking/operated 'sham' pad present/in-use nightly (weeks ~6-8). Objective sleep monitoring for 2 nights. Blood sample (up to 40cc / up to 3 tablespoons) collected.

All participants will complete all parts of the study (i.e. both intervention and control) but the order in which they experience these conditions will be randomized at the end of Baseline week after verifying compliance with study procedures and eligibility to continue.

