6.2.11 Visit 11 (Phase I)

Participant has a fasted blood draw conducted by qualified Clinical Research Center (CRC; Noll Laboratory) staff. This visit (11) may be combined with the previous visit (10) if a participant elects for the blood draw to occur in their personal residence.

- -Participant returns the bedside controller.
- -Participants keep the bed pad portion of the sleep pad system for re-use later in the study.

Above procedures take about 30min 'active' engagement to complete.

6.2.12 Washout and Visit 12

The ~5th study week will consist of a "washout" during which no participants use the functional features of sleep pad system. However, throughout this week, participants do continue 24hr actigraphy monitoring, continue to complete daily sleep diary and device usage survey entries (~2min combined), and continue to complete the weekly REDCap survey all noted in the general summary above.

Note that an optional pause of study activities at the conclusion of the Washout week will be available. Participants are not required to continue passive (actigraphy) monitoring or surveys during any pause period (>1wk). Maximum duration of appropriate pause will be determined by Co-Investigators, but is not anticipated to exceed 10wks.

Total anticipated Washout active study time commitment is 30min.

At the beginning of study week 6, a participant receives again for use the bedside controller, either by delivery (in-person or by mail) or pickup from PSU-UP campus. Because receipt may occur in person, this is considered the "12th visit" although not necessarily requiring a "visit".

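### Section 7.3 names no period term for this two-period crossover, so any common Phase 1-to-Phase 2 drift stays in the paired difference: at equal orders it widens the interval, and at unequal orders it shifts the mean, conditional on that split

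*Combined protocol and SAP*

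**What the plan says.** Section 7.3 gives the method in full: "Primary and secondary outcomes will be compared between sleep pad conditions, within participants, as a change score relative to their own Baseline". It states no model, period or sequence term, interval or effect-size formula, and no other section supplies one.

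Section 6.1 sets out a Baseline in week 1, a first condition in weeks 2-4, Washout in week 5 and the second condition in weeks 6-8. Section 6.2 describes the single Baseline: "Baseline data collection without sleep pad device present/in-use (week ~1) and randomization". Under section 6.2.12, actigraphy, diaries and the weekly survey continue through Washout. No PSG or blood draw is listed there, and section 7.3 does not use Washout as a second baseline.

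Section 6.4.3 describes randomisation to order "with replacement for early withdrawal, and intention to assign 50% of participants to each study condition order". It does not say whether a replacement takes the vacated order. Section 7.1 aims for 10 completers.

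Effect sizes are a stated product of the study. Section 1.1 wants to "calculate the effect sizes of the intervention to inform power and sample size for future studies", and section 7.2 says "This pilot study is being used to determine feasibility and effect sizes". Section 6.2.12 also allows a gap between phases for some participants: "Note that an optional pause of study activities at the conclusion of the Washout week will be available". The pause is not expected to exceed 10 weeks.

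**The concern.** Change from Baseline may look as though it protects against change over time. With one Baseline shared by both phases it does not, because the same number is subtracted twice. If sleep measures tend to move between Phase 1 and Phase 2 for any reason other than the pad, the movement enters the active-minus-sham difference with opposite sign in the two orders.

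Two quantities are exposed. The first is the SD of the paired differences, which sets the confidence interval and, if it is the standardiser, the effect size passed to a later sample-size calculation. The second is the mean difference, if the two orders do not finish with equal numbers.

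**Working it through.** **Inputs from the documents.** One Baseline; two phases; two orders intended 50:50; 10 completers. The plan gives no SD, effect, alpha, power or drift, so it has no figure to reproduce.

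**Assumptions for scale.** SD of the paired difference within an order = 1; true effect tau = 0.40 of that SD; drift d (Phase 2 minus Phase 1, common to all) from 0 to 1 SD; 80% power and two-sided 5% for a later paired study.

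**Step 1: the Baseline cancels.** For absolute change scores, (Active - Baseline) - (Sham - Baseline) = Active - Sham. The expected paired difference is tau - d in the active-first order and tau + d in the sham-first order.

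**Step 2: mean and SD.** With n1 active-first, n2 sham-first and n = n1 + n2:

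- mean = tau + d(n2 - n1)/n
- expected SD² = 1 + d² × 4·n1·n2 / [n(n - 1)]

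**Step 3: five per order.** The mean stays at 0.40. The factor on d² is 4·5·5/(10·9) = 1.111, so the root of the expected SD² at d = 0.5 is sqrt(1 + 1.111 × 0.25) = 1.13. The mean difference still varies with a standard error of 1/sqrt(10) = 0.316, but the unadjusted analysis estimates about 1.13/sqrt(10) = 0.357. That is why the interval is too wide. In the table, large-sample dz is 0.40/sqrt(1 + d²).

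| d (SD) | Root of expected SD² | Large-sample dz | Later paired n | Mean Hedges-corrected dz, n = 10 | Same, period-adjusted |
|---|---|---|---|---|---|
| 0 | 1.00 | 0.400 | 52 | 0.400 | 0.400 |
| 0.25 | 1.03 | 0.388 | 55 | 0.387 | 0.400 |
| 0.5 | 1.13 | 0.358 | 64 | 0.353 | 0.400 |
| 1 | 1.45 | 0.283 | 101 | 0.269 | 0.400 |

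By simulation, the unadjusted 95% interval covers about 97% at d = 0.5 and 99% at d = 1.

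**Step 4: the standardiser matters.** With a Baseline SD there is no shrinkage at 5:5. With a change-score SD (assumed 1) the factor is 1/sqrt(1 + d²/4): 0.99 at d = 0.25 and 0.97 at d = 0.5.

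**Step 5: unequal orders.** The mean shifts by 0.2d in size at 6:4 and 0.4d at 7:3. At d = 0.25 with six active-first, the mean is 0.40 + 0.25 × (4 - 6)/10 = 0.35. With six sham-first it is 0.45. The Hedges-corrected dz is then 0.34 or 0.44, so it can fall below or rise above 0.40.

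**Step 6: how a split could become unequal.** Suppose each replacement's order were drawn 50:50 whatever order was vacated. One withdrawal from 5:5 gives 6:4 with probability 50%. Two withdrawals from the original ten give 6:4 with probability 50% and 7:3 with probability 11%. If replacements take the vacated order, balance is kept.

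**Step 7: total error in dz.** Root-mean-square error of the Hedges-corrected dz around 0.40 at 5:5, unadjusted against adjusted, is 0.346/0.350 at no drift, 0.334/0.350 at 0.25, 0.307/0.349 at 0.5 and 0.261/0.351 at 1 SD. The adjusted estimate is less biased, but not closer to the truth in these cases. Part of this is shrinkage towards zero when the assumed effect is small.

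**The case against.** The strongest reply is that section 7.3 is an outline for a 10-person pilot. It does not exclude a period term; it leaves the whole model open. The documents report no drift and no dropout, the orders are meant to be equal, and sampling error dominates: an observed dz of 0.40 at n = 10 has a 95% interval of -0.26 to 1.04. At 5:5 with drift of 0.25 SD or less, dz falls by only about 3%. All of that stands, and it keeps the point small.

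A reader might infer more than the documents support:

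- **That drift lowers dz in general.** This holds at equal orders with the paired-difference SD as standardiser. At unequal orders dz can rise (step 5).
- **That the plan yields a systematically biased mean.** The shift is conditional on the realised split. Under random withdrawal and 50:50 replacement, n2 - n1 averages zero. A systematic bias would need withdrawal to depend on order, and nothing in the documents says that it does.
- **That adjustment gives a more accurate dz at n = 10.** Step 7 shows that it generally does not.
- **That the optional pause shows drift, or that a period term would deal with it.** The pause only allows a longer gap for some participants. Drift that differs between participants is not removed by a common period effect.

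What remains is that effect sizes are a declared output and the usual crossover term is not stated. Under section 6.4.5 the wider team is unblinded for analysis, so an open choice of model would be made with assignments known.

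**Conclusion.** The point holds as a cheap improvement, not as a failure of the plan. As written, section 7.3 leaves any common drift in the paired difference. At equal orders the mean is sound, the interval is too wide, and a dz scaled by the paired-difference SD is too low relative to a period-adjusted one. The effect is negligible at d = 0.25 SD or less and material only at about 0.5 SD and above. At unequal orders the mean is off by d(n2 - n1)/n for that split, in either direction. Every size given rests on an assumed drift, effect and standardiser. The benefit of a period term is a valid interval and removal of order bias, rather than lower total error in dz.

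**What to change.** State in section 7.3 that:

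1. Each outcome is first reduced to one value per participant per phase. If nightly rows are modelled instead, a participant-by-phase term is included; otherwise the two PSG nights or the daily records would be treated as independent and precision overstated.
2. The model has condition and period as fixed effects and participant as a random or fixed effect. For complete pairs with one value per phase, this is the average of the two order-specific mean differences, with the SD pooled within order (8 df at n = 10).
3. The mean difference is reported with its 95% CI. The standardiser is named, and the effect size is Hedges-corrected (factor 0.903 at 8 df if the within-order SD is used) and given with a CI.
4. Completers are reported by order, and section 6.4.3 says whether a replacement takes the vacated order.
5. The period term does not address carryover, or drift that differs between participants, for example with the optional pause. Reporting pause length by order would let readers judge the latter.

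The cost is wording and one degree of freedom; no new data are needed. For scale, at dz = 1 with no drift, the power of a two-sided 5% test (which the plan does not call for) falls from 80% to 79% at 5:5, 77% at 6:4 and 72% at 7:3. The adjusted dz is also slightly more variable at n = 10.
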